--	--

	
objectives and 168 per group for the secondary objective.
 
Interim analysis:
 
Two planned statistical analyses will be performed:
 
An interim statistical analysis of the data obtained up to Day 28 post third CYD dengue vaccination might be performed once data are available and a database lock has been conducted.
 
A final analysis will be performed once the 6 month safety data have been collected and the final database lock has occurred.
 
No statistical adjustment is necessary because there will be no repeated analyses of the primary objective (as the test will be performed at the time of the first analysis).

--	---

Table of Study Procedures

Phase IIIb Trial; 5 Injections; **Group 1**: 6 Visits and a 6-month follow-up Phone Call, 4 Blood Samples, 18 Months duration per subject, 6 interim phone calls; **Group 2**: 8 Visits and a 6-month follow-up Phone Call, 6 Blood Samples, 19 Months duration per subject, 8 interim phone calls. Interim phone calls will be given 7 days after each injection (PC1, PC2, PC4, PC5, and PC7) and 2 months after blood samples (PC3, PC6, and PC8) during the 6-month period after each vaccination. As per Protocol Amendment 1, only dengue-exposed subjects before the first dengue vaccine injection will be eligible to continue study vaccinations with the CYD dengue vaccine.

Visit (V) Number	Time period prior to Protocol Amendment 1						Time period post Protocol Amendment 1*		
	V01	V02	V03 (Group 2)	V04	V05	V06†‡ (Group 2)	V07**	V08†	Phone Call§
Trial Timelines	D0	M1 (V01+28D)	M2 (V02+28D)	M6 (V01 + 6M)	M7 (V04+28D) (Group 1) (V02+6M) (Group 2)	M8 (V05+28D)	M12 (V01 + 12M) (Group 1) M13 (V02+ 12M) (Group 2)	M13 (V07+28D) (Group 1) M14 (V07+28D) (Group 2)	M18 (V07+6M) (Group 1) M19 (V07+6M) (Group 2)
Time Windows (days)		+14	+14	±20	+14	+14	±20	+14	+30
Informed Consent and assent form (if applicable) signed	X								
Amendment 1 to AF and ICF						X (Amdt 1) (as applicable)	X (Amdt 1) (as applicable)		
Inclusion/Exclusion Criteria	X								
Significant Medical History	X								
History of Dengue Infection/Vaccination	X								
Demography/Body Stature	X								
Physical/Clinical Examination and Temperature**	X	X (Group 2)	X (Group 2)	X	X	X (Group 2)	X	X	
Concomitant Therapy††	X	X	X (Group 2)	X	X	X (Group 2)	X	X	
Urine Pregnancy Test‡‡	X	X (Group 2)		X	X (Group 2)		X		
Randomization	X								
Contraindications		X (Group 2)		X	X (Group 2)	X	X		

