- 9) Record the date of injection, the site and side of injection and the route of administration, as well as the dose number of the vaccine.
- 10) Give the parent(s)/legally acceptable representative(s) a DC for Group 2 and Group 1 (for Group 1 DC for SAE collection only).
- 11) Remind the parent(s)/legally acceptable representative(s) of subjects in Group 2 to bring back the DC when they return for Visit 3 at a specified date and time.
- 12) Remind the parent(s)/legally acceptable representative(s) of subjects in Group 1 to bring back the DC when they return for Visit 4 at a specified date and time.
- 13) Complete the relevant CRF pages for this visit.

Phone Call 2 (PC2) (7 days [+8 days] after Visit 2)

The same procedures as those described for PC1 will be followed.

Visit 3 (Month 2; 28 [+14] days after Visit 2)

This visit is applicable only for subjects in Group 2. These subjects will receive their first dose of CYD dengue vaccine at Visit 2 and will come to Visit 3 for blood sampling. The Investigator or designated study personnel will:

- 1) Check the information entered into the DC by interviewing the subject / subject's parent(s) / legally acceptable representative(s) and request information concerning any medical event, serious or not, that may have occurred since Visit 2.
- 2) Perform a physical examination and record the subject's axillary temperature.
- 3) Check concomitant medications and record every reportable medication ongoing at the time of vaccination.
- 4) Obtain the blood sample (see [Section 7.1](#) for detailed instructions regarding the handling of blood samples).
- 5) Give the parent(s)/legally acceptable representative(s) a DC for SAE collection only.
- 6) Remind the parent(s)/legally acceptable representative(s) to bring back the DC when they return for Visit 4 at a specified date and time.
- 7) Complete the relevant CRF pages for this visit.

Phone Call 3(PC3) (approximately 2 months after Visit 2 for Group1 and 2 months after Visit 3 for Group 2)

The same procedures as those described for PC1 will be followed.

Visit 4 (Month 6; 6 months [+ 20 days] after Visit 1)

The Investigator or designated study personnel will:

- 1) Review the pages of the DC with the parent(s)/legally acceptable representative(s)
- 2) Perform a physical examination and record the subject's axillary temperature
- 3) Collect information regarding the subject's medication status since the previous visit.

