- 4) Perform a urine pregnancy test before injection (for woman of childbearing potential only).
- 5) Review temporary and definitive contraindications to vaccination
- 6) Inject the second dose of Cervarix to all subjects (Groups 1 and 2) and the second dose of CYD dengue vaccine to subjects in Group 1 (6 months post-dose 1).
- 7) Keep the subject under observation for 30 minutes, and record any immediate AE in the source document.
- 8) Record the date of injection(s), the site and side of injection(s) and the route of administration(s), as well as the dose number of the vaccine(s).
- 9) Give the parent(s)/legally acceptable representative(s) a DC.
- 10) Remind the parent(s)/legally acceptable representative(s) to bring back the DC when they return for Visit 5 at a specified date and time.
- 11) Complete the relevant CRF pages for this visit.

Phone Call 4 (PC4) (7 [+8 days] days after Visit 4)

The same procedures as those described for PC1 will be followed.

Visit 5 (Month 7; 6 months /± 20 days/ after Visit 2)

The Investigator or designated study personnel will:

- 1) Review the pages of the DC with the parent(s)/legally acceptable representative(s), including any AEs, medications, or therapy that occurred since vaccination.
- 2) Perform a physical examination and record the subject's axillary temperature
- 3) Check concomitant medications and record every reportable medication ongoing at the time of vaccination.
- 4) Obtain the blood sample (see [Section 7.1](#) for detailed instructions regarding the handling of blood samples).
- 5) For female subjects of childbearing potential, perform a urine pregnancy test before injection (subjects in Group 2 only).
- 6) Review temporary and definitive contraindications to vaccination
- 7) Inject the second dose of CYD dengue vaccine to subjects in Group 2 (6 months post dose 1).
- 8) Keep the subject under observation for 30 minutes, and record any immediate AE in the source document (Group 2).
- 9) Record the date of injection, the site and side of injection and the route of administration, as well as the dose number of the vaccine (Group 2).

- 10) Give the parent(s)/legally acceptable representative(s) a DC for Group 2 and Group 1 (for Group 1 DC for SAE collection only).
- 11) Remind the parent(s)/legally acceptable representative(s) of subjects in Group 2 to bring back the DC when they return for Visit 6 at a specified date and time.

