- 12) Remind the parent(s)/legally acceptable representative(s) of subjects in Group 1 to bring back the DC when they return for Visit 7 at a specified date and time.
- 13) Complete the relevant CRF pages for this visit.

Phone Call 5 (PC5) (7 days [+8 days] after Visit 5)

The same procedures as those described for PC1 will be followed.

Visit 6 (Month 8; 28 [+14] days after Visit 5)

This visit is applicable only for subjects in Group 2 and the same procedures as those described for Visit 3 will be followed.

Phone Call 6 (PC6) (2 months after Visit 5 and 2 months after Visit 6)

The same procedures as those described for PC1 will be followed.

Additional Unscheduled Visit (V00)/Phone Call (PC00)- As per Protocol Amendment 1

This unscheduled visit/phone call is to take place between Visit 5 (subjects from Group 1) or Visit 6 (subjects from Group 2) and Visit 7. During this visit/phone call, subjects will be informed by the mean of the “Dear Participant Letter” about the results of the exploratory analyses, ie, 1° the increased risk of hospitalized or severe dengue for those unexposed to dengue infection prior to the first injection with the CYD dengue vaccine; and 2° the confirmed and sustained benefit of vaccination in dengue exposed subjects. Subjects will be informed about their dengue serostatus at baseline if available.

At the latest, this visit will take place at the same time as the next subject’s scheduled visit.

Visit 7 (initially planned at Month 12 [+20 days] after Visit 1 (Group 1) or Month 12 [+20 days] after Visit 2 (Group 2)

For subjects who will return at V07 after the suspension of vaccination

- 1) Present the changes brought to the study design to the subject and the subject's parent(s)/legally acceptable representative(s) in more detail, answer any of their questions, and ensure that they have been informed of all aspects that are relevant to their decision to continue participating in the study
- 2) Have the subject and the subject's parent(s) /legally acceptable representative(s), date and sign the new AF and/or ICF version, as applicable
- 3) Depending on subject's serostatus at baseline:

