7.1 Sample Collection

7.1.1 Serum Samples for Neutralizing Ab Assessment

As per Protocol Amendment 1, dengue exposed subjects who will continue in the study and consent to receive the remaining CYD vaccine injection will provide all blood samples as initially planned. All other subjects will not provide the blood samples initially planned. At Visits 1, 2, 3, 5, 6, and 8, 4 to 6 mL of blood will be collected in tubes provided by or recommended by the Sponsor. Immediately prior to the blood draw, the staff member performing the procedure will verify the subject’s identity; will write the assigned subject’s number on the pre-printed label that contains that subject’s number and the sampling stage; and will attach the label to the tube. Blood is to be taken from the limb opposite to the one that will be used for vaccination for sequential injection (Group 2), or from the limb opposite to the one that will be used for CYD dengue vaccine injection for concomitant injection (Group 1).

Table 7.1: Blood sampling volume (mL) per visit

Visit Number	V01	V02	V03	V05	V06	V08† M13 (V07+28D) (Group 1) M14 (V07+28D) (Group 2)
Trial Timelines (Days/Months)	D0	M1 (V01+28D)	M2 (V02+28D)	M7 (V04+28D)	M8 (V05+28D)	+14
Time Windows (Days)		+14	+14	+14	+14	+14
Dengue Neutralizing Abs	4 (Group 1)	4 (Both groups)	4 (Group 2)	4 (Group 1)	4 (Group 2)	4 (Both groups)
HPV Abs	2 (Both groups)	2 (Both groups)		2 (Both groups)		
TOTAL (mL)	6 (Group 1) 2 (Group 2)	6 (Group 1) 6 (Group 2)	0 (Group 1) 4 (Group 2)	6 (Group 1) 2 (Group 2)	0 (Group 1) 4 (Group 2)	4 (Group 1) 4 (Group 2)

† BL post Protocol Amendment 1 (dengue exposed subjects who consent to continue in the study and receive the next injection(s) of CYD dengue vaccine)

7.1.2 Blood Sample for Virological Confirmation of Hospitalized Suspected Dengue Case and Assessment of Disease Severity

In the event of hospitalized suspected dengue case, one 3 mL acute blood sample will be collected (within the 5 days after the fever onset) as presented in [Table 7.2](#). The acute blood sample for all hospitalized suspected dengue cases should be collected within the pre-specified timeframe as described above. If this cannot be accomplished, this sample should still be obtained as soon as possible thereafter, for IDMC severity assessment. This blood sample will be used to confirm whether a hospitalized suspected dengue case is dengue disease or not, and upon confirmation of infection, to identify dengue virus serotype.

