9.1.1.2 Immunogenicity Assessment Methods

HPV Abs

The Ab response to HPV will be performed at Sanofi Pasteur GCI, Swiftwater, USA, or GCI outsourced laboratory. The HPV16/18 virus-like particle-based enzyme linked immunosorbent assay (VLP-ELISA) is performed using serial dilutions of serum samples and standards added to HPV VLP-coated ELISA microtiter plates. A peroxidase-conjugated anti-human IgG polyclonal antibody, enzyme substrate, and chromogen are added; reactions are then stopped. Optical density (OD) at 620 nm (background) is read and subtracted from OD at 450 nm. Antibody levels in ELISA units (EU)/mL are calculated by interpolating OD values from the standard curve.

This assay will be performed on blood samples taken from V01, V02 and V05.

Dengue Neutralizing Abs

Dengue neutralizing Ab levels will be measured by PRNT₅₀ (using parental dengue virus strains of CYD dengue vaccine constructs) by Sanofi Pasteur GCI, Swiftwater, USA (or outsourced with a GCI selected external laboratory).

Serial, two-fold dilutions of serum to be tested (previously heat-inactivated) are mixed with a constant challenge-dose of each dengue virus serotype 1, 2, 3 or 4 (expressed as plaque-forming unit [PFU]/mL). The mixtures are inoculated into wells of a microplate with confluent Vero cell monolayers. After adsorption, cell monolayers are incubated for a few days. The presence of dengue virus infected cells is indicated by formation of plaques. A reduction in virus infectivity due to neutralization by Ab present in serum samples is detected. The reported value (end point neutralization titer) represents the highest dilution of serum at which $\geq 50\%$ of dengue challenge virus (in plaque counts) is neutralized when compared to the mean viral plaque count in the negative control wells which represents the 100% virus load. The end point neutralization titers are presented as continuous values. The lower limit of quantitation (LLOQ) of the assay is 10 (1/dilution [dil]).

This assay will be performed on each blood samples taken at V01 (Group 1 only), V02, V03 (Group 2 only), V05 (Group 1 only), V06 (Group 2 only), and V08.

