12.2.2 Per-Protocol Analysis Set

Two per-protocol analysis sets will be defined: one for Cervarix (PPX) and one for CYD dengue vaccine (PPC). The per-protocol analysis sets are subsets of the FAS.

PPX

The subjects presenting with at least one of the following relevant protocol deviations will be excluded from the PPX:

- Subject did not meet all protocol-specified inclusion criteria or met at least one of the protocol-specified exclusion criteria
- Subjects identified as dengue unexposed (seronegative) at baseline
- Subject is seropositive at baseline for Cervarix (ie, at least one Ab levels against Cervarix HPV antigens > LLOQ at baseline)
- Subject did not complete the vaccination schedule (until V05 for Group 1, V06 for Group 2)
- Subject received a vaccine other than the one that she was randomized to receive (until V05 for Group 1, V06 for Group 2)
- Administration of vaccine was not done as per-protocol (site and route of administration)

- Subject did not receive vaccine in the proper time window (until V05 for Group 1, V06 for Group 2)
- Subject did not provide after the 2nd dose of Cervarix a post-dose serology sample in the proper time window or a post-dose serology sample was not drawn (V05 for Group 1, V06 for Group 2)
- Subject received a protocol-prohibited medication (prohibited therapies/medications/vaccines are indicated in [Section 6.7](#)) (until V05 for Group 1, V06 for Group 2)
- Subject's serology sample did not produce a valid test result, ie, no Cervarix antigen titer available

PPC

The subjects presenting with at least one of the following relevant protocol deviations will be excluded from the PPC:

- Subject did not meet all protocol-specified inclusion criteria or met at least one of the protocol-specified exclusion criteria
- Subjects identified as dengue unexposed (seronegative) at baseline
- Subject did not complete the vaccination schedule
- Subject received a vaccine other than the one that she was randomized to receive
- Administration of vaccines was not done as per-protocol (site and route of administration)
- Subject did not receive vaccines in the proper time window
- Subject did not provide after the 3rd dose of CYD dengue vaccine a post-dose serology sample in the proper time window or a post-dose serology sample was not drawn (V08, M13 for Group 1 and M14 for Group 2)
- Subject received a protocol-prohibited medication (prohibited therapies/medications/vaccines are indicated in [Section 6.7](#)) (until V07)

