#### **PPX**

The subjects presenting with at least one of the following relevant protocol deviations will be excluded from the PPX:

- Subject did not meet all protocol-specified inclusion criteria or met at least one of the protocol-specified exclusion criteria
- Subjects identified as dengue non-immune subjects (seronegative) at baseline
- Subject is seropositive at baseline for Cervarix (ie, at least one Ab levels against Cervarix HPV antigens > LLOQ at baseline)
- Subject did not complete the Cervarix vaccination schedule (until V05 for Group 1, V06 for Group 2)
- Subject received a vaccine other than the one that she was randomized to receive (until V05 for Group 1, V06 for Group 2)
- Administration of vaccine was not done as per-protocol (site and route of administration)

- Subject did not receive vaccine in the proper time window (until V05 for Group 1, V06 for Group 2)
- Subject did not provide after the 2nd dose of Cervarix a post-dose serology sample in the proper time window or a post-dose serology sample was not drawn (V05 for Group 1, V06 for Group 2)
- Subject received a protocol-prohibited medication (prohibited therapies/medications/vaccines are indicated in the Protocol Section 6.7) (until V05 for Group 1, V06 for Group 2)
- Subject's serology sample did not produce a valid test result, ie, no Cervarix antigen titer available

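### The PPX post-dose-2 sample rule names V06 for Group 2, where no HPV assay is run; the HPV sample actually analysed is at V05 in both groups

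*SAP*

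**What the plan says.** **The rule.** Protocol 12.2.2 excludes from PPX where "Subject did not provide after the 2nd dose of Cervarix a post-dose serology sample in the proper time window", or where no such sample exists. SAP 5.2.2 has the same criterion. Both attach the visits: "post-dose serology sample was not drawn (V05 for Group 1, V06 for Group 2").

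**Where HPV is measured.** Protocol 9.1.1.2, on the HPV ELISA: "This assay will be performed on blood samples taken from V01, V02 and V05". Section 5.1.3 places the HPV blood at D0, M1 and M7. Table 7.1 lists no HPV volume at V06; the total there is "0 (Group 1) 4 (Group 2") mL, all for dengue neutralization.

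**When V05 falls.**
- Protocol Table of Study Procedures, repeated in SAP Table 3.1, window +14 days: "M7 (V04+28D) (Group 1) (V02+6M) (Group 2").
- Protocol 5.1.4, with no split by group: "Visit 5 (Month 7; 6 months /± 20 days/ after Visit 2").
- Protocol Table 7.1, with no split by group: 28 days after V04, window +14.

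**When V06 falls.** Protocol 5.1.4: "Visit 6 (Month 8; 28 [+14] days after Visit 5"), Group 2 only.

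**Use of PPX.** SAP 5.2.5 makes PPX the set for the Cervarix non-inferiority tests. SAP 5.5 allows testing only with at least 163 evaluable subjects per group (co-primary) and 168 (secondary).

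**The concern.** A per-protocol sample rule should check the sample that supplies the endpoint. In Group 1 it does. In Group 2 it checks a tube drawn four to six weeks later for a different assay. Two errors follow if the bullet is programmed as printed: a subject with a usable, on-time HPV result can be removed for a reason unrelated to that result, and a subject whose HPV sample was mistimed can pass this bullet.

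Both occur in one arm only, in the set that carries the co-primary HPV GMT comparison and the seroconversion comparison. The PPX count also feeds the decision on whether to test at all, and at Amendment 1 the number of seropositive subjects per group was not known. The SAP drops the separate full analysis set of exposed subjects on which the protocol would have confirmed the tests (SAP 5.7), so PPX membership carries more weight than it did in the protocol.

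**Working it through.** **1. The plan's own HPV power.** Inputs from SAP 5.5 and Table 5.2: SD 0.4, margin 0.301 log10, one-sided 0.025, true ratio 1. Power = Φ(0.301 / SE − 1.96), with SE = 0.4 × √(2/n).
- n = 163: SE = 0.0443; 0.301/0.0443 − 1.96 = 4.83; power above 99.99%.
- n = 204: SE = 0.0396; 0.301/0.0396 − 1.96 = 5.64; power above 99.99%.

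Both agree with the stated >99.9%. The point is not about HPV power.

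**2. Which sample the rule reaches.**

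| | Group 1 | Group 2 |
|---|---|---|
| HPV sample after Cervarix dose 2 | V05 | V05 |
| Visit named in the PPX sample bullet | V05 | V06 |
| Assay at the named visit | HPV and dengue | dengue only |

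**3. Days from Cervarix dose 2 (V04) to the HPV sample (V05), by SAP Table 3.1.**

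Group 1: V05 = V04 + 28, window +14, so 28 to 42 days.

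Group 2: let V02 = V01 + a, V04 = V01 + 6 months + b, and V05 = V02 + 6 months + c, with a from 28 to 42, b from −20 to +20 and c from 0 to 14. The six months cancel, so V05 − V04 = a + c − b.
- Minimum: 28 + 0 − 20 = 8 days.
- Maximum: 42 + 14 + 20 = 76 days.
- If the minimum of 28 days between the vaccines (Protocol 5.1.2, SAP 1) is enforced: 28 to 76 days.
- On the nominal schedule: 28 days, as in Group 1.

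**4. The other two timings.** Table 7.1 gives 28 to 42 days in both groups. The V05 window in Section 5.1.4, with V04 at ±20, gives 28 − 20 − 20 = −12 to 42 + 20 + 20 = 82 days. That cannot serve as a post-dose window without the 28-day minimum. Neither source splits V05 by group, so neither creates an arm difference by itself. Section 5.1.4 also prints V04 differently from the tables: "Visit 4 (Month 6; 6 months [+ 20 days] after Visit 1").

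**5. Days from dose 2 to V06 in Group 2.** From step 3, 8 + 28 = 36 to 76 + 42 = 118 days, nominally 28 + 28 = 56. That is the sample the bullet checks against an endpoint set at 28 days.

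**6. Do other PPX bullets repair this?**
- The last bullet removes anyone with no usable Cervarix titer. It catches a missing V05 result, not a mistimed one.
- The vaccine-window bullet reaches Group 2's V05 because CYD dose 2 is given there. It limits V02, V04 and V05 to their own windows, but the table ties V05 to V02, so what passes is the 8 to 76 days of step 3.
- Neither bullet restores a subject removed because of her V06 sample.

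**The case against.** The best defence is that this is a label slip. The bullet asks for a sample after the second Cervarix dose, in a set built for Cervarix, and only V05 fits; harm requires someone to program the parenthesis literally. That is plausible, but the parenthesis is the only part that names a visit, it appears in both documents, and the SAP edited a neighbouring bullet while leaving this one. The correction is still needed.

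Several counter-arguments stand and limit the point:
- The SAP carries only one V05 timing, Table 3.1. The differing entries are in the protocol, so a reader should not infer that the SAP leaves three schedules open.
- The protocol places CYD dose 2 in Group 2 at M6 plus 28 days, and HPV blood 28 days after each Cervarix dose. The nominal day is 28 in both arms; 8 to 76 is what the windows permit, not what happened.
- All Group 2 subjects had completed V06 by Amendment 1, so only late or undrawn V06 samples matter.
- The co-primary threshold also needs the CYD per-protocol set, which requires dose 3 in window and a V08 sample after a pause of about six months, and may well be the smaller set.
- Anyone removed from PPX still appears in the full analysis set results by baseline dengue status.

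A reader might infer that HPV titers are compared at different times in the two arms and that the GMT ratio is therefore biased. The documents do not support that: the HPV result comes from V05 in both groups, no titer kinetics are given, and actual visit dates are not in the plan. Nor do they show that the threshold would be missed, since no rate of late or undrawn V06 samples is given.

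**Conclusion.** The PPX sample criterion is wrong as written for Group 2. It names a dengue-only visit, can exclude subjects with a valid V05 HPV result, and leaves the timing of that result unchecked by the bullet meant to check it. Group 1 is not affected in this way, so the arms are screened unequally for the co-primary HPV GMT and the seroconversion tests.

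The permitted sampling interval after dose 2 is 8 to 76 days in Group 2 (28 to 76 with the 28-day minimum) against 28 to 42 in Group 1, taking SAP Table 3.1 as governing. No size or direction of bias is claimed. HPV GMT power stays above 99.9% at 163 per group. The effect on the 163/168 threshold is unknown; the 168 figure depends on PPX most directly. This is a correction to make before lock, not evidence that the comparison is invalid.

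**What to change.** 1. In the PPX sample bullet of SAP 5.2.2, change Group 2's visit from V06 to V05, and note the departure from Protocol 12.2.2 in SAP 5.7.
2. State in the same bullet the V05 sample window that applies to PPX. Table 3.1 is the natural source; if it governs, say whether the 28-day minimum also applies, and that Protocol 5.1.4 and Table 7.1 do not define the window.
3. Tabulate actual days from Cervarix dose 2 to the V05 HPV sample, by arm, for PPX and the full analysis set.

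Step 1 alone points the rule at the right sample but does not bound days since dose 2, because Table 3.1 ties Group 2's V05 to V02; hence steps 2 and 3. Imposing 28 to 42 days as a hard exclusion is not advised: under Table 3.1 it would tighten the rule for Group 2 only, after randomization.

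The cost is two lines of SAP text and one table. Injection and sampling dates are already recorded (Protocol 5.1.4 and 7.2). Completed visits cannot be re-timed.
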